6.1.2.2. Visit 3 (Day 120; ~4 Months)

Patients will return to the Research Site for Visit 3 on Day 120 ± 10 days.

The following procedures will be performed:

- Perform physical examination
- Obtain weight
- Obtain vital signs (systolic and diastolic blood pressure, heart rate, respiratory rate, and body temperature)
- Obtain fasting blood samples for:
 - Chemistry and hematology testing
 - Lipid profile

- Review study drug compliance by unused capsule count; discuss with and counsel patients about compliance if needed
- Administer study drug - Note: Study drug should be taken orally with food following the collection of all fasting blood samples
- Assess and record efficacy events
- Assess for and record adverse events
- Record concomitant medication(s)
- Instruct patient:
 - To bring all study supplies with them to the next visit
 - Not to take study drug on the morning of their next visit
 - To fast for ≥ 10 hours prior to the next visit

6.1.2.3. Visits 4, 5, 6, 7, 8 and 9

At Visit 4: Day 360 ± 10 ; Visit 5: Day 720 ± 10 ; Visit 6: Day 1080 ± 10 ; Visit 7: Day 1440 ± 10 , Visit 8: Day 1800 ± 10 , Visit 9: Day 2160 ± 10) the following procedures will be performed:

- Perform physical examination
- Obtain weight
- Obtain vital signs (systolic and diastolic blood pressure, heart rate, respiratory rate, and body temperature)
- Measure waist circumference (collected at Visit 5 only)
- Obtain a 12-lead ECG
- Obtain fasting blood samples for:
 - Chemistry and hematology testing
 - Lipid profile
 - Biomarker assays (collected at Visit 5 only)
 - Archiving (in countries and at sites approved by IRB/IEC and dependent on country regulations)
- Review study drug compliance by unused capsule count; discuss with and counsel patients about compliance if needed
- Administer study drug - Note: Study drug should be taken orally with food following the collection of all fasting blood samples
- Assess and record efficacy events
- Assess for and record adverse events
- Record concomitant medication(s)
- Instruct patient:

- To bring all study supplies with them to the next visit
- Not to take study drug on the morning of their next visit
- To fast for ≥ 10 hours prior to the next visit

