4.7 Efficacy Analyses

4.7.1 Primary Efficacy Endpoint

4.7.1.1 Primary Analysis

The primary efficacy endpoint is the time from randomization to the first occurrence of any component of the composite of the following adjudicated clinical events:

- CV death,
- Nonfatal MI (including silent MI; ECGs will be performed annually for the detection of silent MIs),
- Nonfatal stroke,
- Coronary revascularization,
- Unstable angina determined to be caused by myocardial ischemia by invasive/non-invasive testing and requiring emergent hospitalization.

All observed data that are positively adjudicated by the CEC, including data after discontinuation of study treatment for patients who discontinue study drug prematurely, will be included in the primary analysis.

Suspected endpoint events are adjudicated by the CEC without knowledge of the treatment. Counts and Kaplan-Meier estimates of the percentage of patients experiencing each type of adjudicated event by study completion, along with overall counts for each type, will be presented by treatment arm. A separate table of the number of events that are ruled out by the CEC will also be displayed.

The event time will be calculated as the (date of first event – date of randomization + 1 day) for patients who experience one or more of the primary endpoint events. The following provides detailed considerations for determining the date of event/date of censoring:

- Patients who do not experience a primary efficacy event prior to the end of the study or withdrawal from the study early without a preceding primary efficacy event will be censored at the date of their last visit/phone contact.
- Patients who die with an adjudicated undetermined cause of death and without a preceding endpoint event will be considered to have an adjudicated CV death and this will be included as an event in the primary analysis.

- In view of the 90-day monitoring period for CV events, patients who have a non-CV death within 90 days of last contact without having had an earlier CV event will be censored at the time of death. Patients who have a non-CV death more than 90 days after last contact without having had an earlier CV event will be censored at the date of their last visit/phone contact.
- The primary analysis of silent MI will assume that all silent MIs occurred on the date of the first tracing indicative of a silent MI.

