4.7.3.1 Key Secondary Efficacy Endpoint

If the primary analysis is statistically significant, then the key secondary efficacy endpoint, which is the time from randomization to the first occurrence of the composite of CV death, nonfatal MI (including silent MI), or nonfatal stroke will be tested first.

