4. OTHER SENSITIVITY, SUPPORTIVE AND EXPLORATORY ANALYSES FOR THE PRIMARY EFFICACY ENDPOINT

This section relates to Section 4.7.1.2 of version 1 of the SAP dated 08 July 2016.

Time-to-event analyses as done for the primary analysis will be carried out at 1-year and 2-year landmarks for the intent-to-treat (ITT) Population. For each landmark, the log-rank test, stratified by stratification variables at randomization (cardiovascular [CV] risk category, use of ezetimibe, and geographical region [Westernized, Eastern European, and Asia Pacific countries]), will be used to compare the time-to-event between treatment groups. Similarly, hazard ratios and 95% confidence intervals will be determined using Cox proportional hazards modelling. Patients without events prior to the landmark time will be censored.

For the recurrent CV events analyses based on 5-component Major Adverse Cardiovascular Events (MACE) (CV death, non-fatal myocardial infarction [MI], non-fatal stroke, unstable angina requiring hospitalization, or coronary revascularization), in addition to the Anderson and Gill and the Li and Lagakos methods specified in the SAP dated 08 July 2016, the total CV event counts will be analyzed using a Negative Binomial Model ([Rogers 2012](#), [Rogers 2014](#), and [Claggett 2018](#)). It will be implemented using SAS Proc Genmod with a log link function, log exposure time as offset, and treatment group and randomization strata as factors.

As additional sensitivity analysis for the primary composite endpoint will be carried out, namely, an on-treatment analysis which includes primary event onset up to 0 and 30-days after permanent discontinuation of study drug.

All SAP Addendum efficacy analyses are considered exploratory and are not included in the formal SAP testing scheme.

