6. ANALYSIS OF TERTIARY ENDPOINTS

This section relates to Section 4.7.4 of version 1 of the SAP dated 08 July 2016.

The following clinical events that are positively adjudicated by the Clinical Endpoint Committee (CEC) will be analyzed as tertiary endpoints for the ITT Population:

- Composite of total mortality, or new congestive heart failure (CHF)
- Composite of CV death, or new CHF
- Sudden cardiac death
- Peripheral artery disease (PAD)
- Atrial fibrillation, or atrial flutter

These tertiary endpoints will be analysed similarly as for the primary composite endpoint.

In addition, the following will be analysed as tertiary endpoints for the ITT Population:

- Relationship between on-treatment high-sensitivity C-reactive protein (hsCRP) and the primary and key secondary endpoints
- Relationship between on-treatment serum eicosapentaenoic acid (EPA) and the primary and key secondary endpoints

To assess the relationship between on-treatment hsCRP and the primary and key secondary endpoints, subgroup analyses will be carried out as done for the ITT population for patients grouped according to values greater or equal to or less than 2 mg/dL at baseline and at 2 years.

To assess the relationship between on-treatment serum EPA and the primary and key secondary endpoints, Kaplan-Meier (KM) curves will be produced for AMR101 treated patients grouped into tertiles based on their values at year 1 and will be compared with the placebo-treated patients.

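### SAP Addendum section 6 compares AMR101 patients who reach a year-1 EPA sample with placebo patients who need not, which tilts the EPA curves modestly toward AMR101

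*Combined protocol and SAP*

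**What the plan says.** SAP Addendum section 6 introduces the biomarker analyses with "In addition, the following will be analysed as tertiary endpoints for the ITT Population" and lists "Relationship between on-treatment serum eicosapentaenoic acid (EPA) and the primary and key secondary endpoints". The method for EPA is Kaplan-Meier curves for "AMR101 treated patients grouped into tertiles based on their values at year 1 and will be compared with the placebo-treated patients". No time origin, hazard ratio, test or alpha level is given for it.

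Both endpoints run from randomization. SAP 4.7.1.1: "The primary efficacy endpoint is the time from randomization to the first occurrence of any component of the composite". SAP 4.7.3.1, for the key secondary endpoint: "which is the time from randomization to the first occurrence of the composite of CV death, nonfatal MI (including silent MI), or nonfatal stroke".

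EPA is not among the routine biomarker assays in protocol 6.3.1.4 (hs-CRP, apo B, hsTnT). Serum fatty acids appear in protocol 6.3.1.5 as a possible use of archived serum. The schedule for Visits 4 to 9 (protocol 6.1.2.3) lists that sample as "Archiving (in countries and at sites approved by IRB/IEC and dependent on country regulations".

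The same Addendum section analyses hsCRP by subgroup, with "patients grouped according to values greater or equal to or less than 2 mg/dL at baseline and at 2 years".

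Addendum sections 2 and 4 class all Addendum efficacy analyses as exploratory and outside the formal testing scheme. Section 2 also commits to reporting them in the clinical study report.

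**The concern.** Membership of an EPA tertile is decided by something that happens at year 1. To have a value, an AMR101 patient must be alive, still attending and sampled at about day 360. If follow-up is then counted from randomization, the first year is guaranteed free of death for every tertile member. The placebo group carries no such guarantee. This is immortal-time bias, and here it can only flatter AMR101.

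Two provisions elsewhere might have dealt with it, and neither does:

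- The 1- and 2-year landmarks in Addendum sections 4 and 5 shorten follow-up: "Patients without events prior to the landmark time will be censored". They do not select patients event-free at year 1 and restart the clock, and they are not applied to the EPA curves.
- SAP 4.7.4 enters post-baseline biomarkers as time-dependent covariates in a Cox model, which would be a suitable method. The EPA paragraph does not call on it.

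What is at stake is how the EPA figure is read. Protocol section 1.4 (Dose Selection) cites achieved plasma EPA among the reasons for choosing 4 g/day, so readers may take curves by achieved EPA as evidence about mechanism.

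**Working it through.** **Inputs from the documents** (protocol 12.3, SAP 4.1, iSAP 2): 7990 patients randomized 1:1, so 3995 per arm; control hazard 0.053 per year; accrual 20/40/20/19/1% over 4.2 years; study length 6.5 years; no dropout; HR 0.85; 1612 events.

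**Assumptions not in the documents:** the share *f* of first-year primary events that prevent a year-1 sample (mainly because they are fatal), taken as 10%, 15% and 25%; and, in the simulation, non-CV death at 0.8% per year.

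**Step 1. The plan's own figures.** The plan gives no figure for the EPA analysis, so the design figures were checked first. Schoenfeld's formula at HR 0.85, one-sided 2.5% and 90% power gives 1592 events, against 1612 stated. With the stated Z boundaries 2.669, 2.289 and 2.031, power at 1612 events is 0.897 and one-sided alpha is 0.0250, as in iSAP Table 1. Expected events at HR 0.85 for N = 7990 are 1601. The inputs are therefore a sound base.

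**Step 2. First-year and total events per arm, inert drug.**

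- Before day 360: 3995 × (1 − exp(−0.053 × 360/365.25)) = 203.
- Over the whole study, averaging over the stated accrual: 858.
- Share before the year-1 sample: 203/858 = 0.237, about 24%.

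**Step 3. Spurious hazard ratio.** Dropping a fraction *f* of first-year events from AMR101 only removes *f* × 203 events and little person-time, so HR ≈ 1 − *f* × 0.237.

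| *f* | AMR101 events dropped | Approximate HR | Simulated HR |
|---|---|---|---|
| 10% | 20 | 0.976 | 0.975 |
| 15% | 31 | 0.964 | 0.965 |
| 25% | 51 | 0.941 | 0.942 |

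The last column is a null simulation of 2000 trials per scenario. A separate large-sample calculation without non-CV death gave 0.976 at *f* = 0.10, 0.953 at 0.20 and 0.931 at 0.30. If every first-year event prevented sampling (*f* = 1), it gave 0.765. That is a ceiling, not an estimate.

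**Step 4. False-positive rate if the curves were tested.** With *d*₁ and *d*₀ events, the shift in Z is |ln HR| × √(*d*₁*d*₀/(*d*₁ + *d*₀)), and the one-sided 2.5% rejection rate is Φ(−1.96 + shift). At *f* = 10%:

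- Tertiles pooled: *d*₁ = 838, *d*₀ = 858; shift = 0.024 × 20.6 = 0.49; rate about 7%.
- One tertile: *d*₁ = 838/3 = 279, *d*₀ = 858; shift = 0.024 × 14.5 = 0.35; rate about 5%.

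Simulated rates:

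| *f* | One tertile v placebo | Tertiles pooled |
|---|---|---|
| 10% | 5% | 7% |
| 15% | 7% | 11% |
| 25% | 14% | 23% |

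**Step 5. The remedy.** With both arms started at year 1 among patients event-free and in follow-up, the simulated null HR is 1.00 with about 2.5% false positives. With a true HR of 0.85, the same design returns 0.85.

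**Step 6. Year-2 hsCRP.** Requiring survival to year 2 in both arms gives a null HR of 1.00 and 2 to 3% false positives (600 trials per scenario). That grouping does not tilt toward either arm.

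**The case against.** **The comparator is inferred.** The EPA sentence does not say that all placebo patients are used, or that time runs from randomization. Both follow from the ITT heading, the endpoint definitions and the absence of any restriction. If a year-1 start was intended, the repair is a clarification. That is fair, but a programmer following the text would produce the biased version.

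**Most primary components are nonfatal.** Protocol 11.1 says an outcome event is not a valid reason to stop study drug, so a patient with a first-year revascularization can still give a sample. This stands, and it is why the plausible hazard ratios lie near 0.94 to 0.98 and not near 0.765.

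**No pooled comparison or test is planned.** This also stands. The per-tertile rates are closer to what is specified than the pooled ones, and both describe what would happen if a test were attached to the curves.

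**The shift does not create a gradient.** All three tertiles carry the same survival condition, so it displaces each against placebo without by itself separating high from low EPA. A reader might infer that an inert drug would show an exposure-response trend; this mechanism does not support that.

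**The hsCRP analysis looks similar.** A reader might extend the bias to it. The documents do not support this, because both arms are grouped by the same rule. Its separate weakness is that events before year 2 precede the value used for grouping.

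**Archive sites.** Sampling only at permitted sites means tertile members and placebo patients may come from different site mixes. A reader might count this as further bias toward AMR101, but nothing in the documents shows its direction.

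**Conclusion.** The point holds for the EPA tertile curves. As written, first-year deaths are excluded from AMR101 and counted on placebo, and the effect always favours AMR101. It is small to moderate: a spurious hazard ratio of about 0.98, 0.97 or 0.94, with false positives of about 5%, 7% or 14% per tertile comparison, if 10%, 15% or 25% of primary events are fatal. These figures rest on the assumed fatal share, the assumed non-CV death rate of 0.8% per year, the design event rate and accrual, and the inferred time origin. The key secondary endpoint was not simulated. CV death is probably a larger share of it, so the bias there is probably larger.

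A reader might conclude that the trial's efficacy claim is compromised. It is not: the primary test, the secondary hierarchy and their type I error do not depend on this analysis. The reason to act is that a one-directional error would otherwise appear in the clinical study report. It is a cheap improvement to an exploratory analysis, not an essential correction.

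**What to change.** Amend the EPA paragraph of SAP Addendum section 6 before database lock:

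- Start the curves at Visit 4 in both arms.
- Include only patients who at that visit are alive, in follow-up, free of the endpoint being analysed and have an archived Visit 4 sample, with the same rule for placebo as for AMR101. This also aligns the site mix and removes events that precede the EPA value.
- Alternatively, enter EPA as a time-dependent covariate from its sampling date, as SAP 4.7.4 does for other biomarkers.
- State that tertile-versus-placebo contrasts remain non-randomized after either change, because tertile membership reflects adherence and patient characteristics.
- For the year-2 hsCRP grouping, apply the same construction at Visit 5 so that no counted event precedes the grouping value. The baseline hsCRP grouping needs no change.

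The cost is wording and programming. The EPA analysis loses the events before year 1, about 24% of primary events; no confirmatory analysis is affected.

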7. EXPLORATORY ANALYSIS OF SUBGROUPS

This section relates to Section 4.7.5 of version 1 of the SAP dated 08 July 2016.

The following will be added to the subgroup analyses:

- Baseline Hemoglobin A1c (HbA1c) value (<6.5%, ≥6.5%)

- Baseline PAD
- Baseline triglyceride (TG) levels ≥ 150 mg/dL with high-density lipoprotein cholesterol (HDL-C) levels ≤ 40 mg/dL for males and ≤ 50 mg/dL for females

Subgroup analyses of the primary and key secondary endpoints will be performed as described for the primary endpoint. For each subgroup, Kaplan-Meier estimates, the log-rank test stratified by stratification factors used at randomization (except where the subgroup is a stratification factor), and hazard ratios (HRs) and confidence intervals (CIs) from the Cox proportional hazards model as specified for the primary efficacy endpoint, will be summarized by treatment group.

8. ADVERSE EVENTS

This section relates to Section 4.8.1 of version 1 of the SAP dated 08 July 2016.

In addition to the treatment-emergent adverse events analyses specified in the SAP dated 08 Jul 2016, the following analyses will be performed:

- All adverse events (AEs) (serious and non-serious)
 - Treatment-emergent adverse event (TEAE) by high level group term (HLGT)
 - TEAE by high level term (HLT)
 - TEAE by system organ class (SOC), HLGT, HLT, and preferred term (PT) (4-level table)
- All serious AEs (SAEs)
 - Treatment emergent SAE by HLGT
 - Treatment emergent SAE by HLT
 - Treatment emergent SAE by SOC, HLGT, HLT, and PT (4-level table)

9. CLINICAL LABORATORY EVALUATION

This section relates to Section 4.8.2 of version 1 of the SAP dated 08 July 2016.

The criteria for potentially clinically significant (PCS) laboratory values are provided in [Table 1](#) and [Table 2](#) of [Appendix A](#). A treatment-emergent PCS high value at any time will be defined as a change from a value less than or equal to the upper reference limit at baseline to a PCS high value at any post-baseline measurement. A treatment-emergent PCS low value at any time will be defined as a change from a value greater than or equal to the lower reference limit at baseline to a PCS low value at any post-baseline measurement. Number (%) of patients with any post-baseline PCS laboratory values will be summarized by treatment group. A listing of patients with PCS laboratory values at any time, i.e., baseline or at any post-baseline visit, will be included.

Drug-Induced Liver Injury (DILI)

Potential DILI cases will be investigated through the following analyses:

- A graph of distribution of peak values of alanine aminotransferase (ALT) versus peak values of total bilirubin (TBL) during the treatment period will be presented, using a logarithmic scale. In the graph, for each patient, the peak TBL times the Upper Limit of Normal (ULN) will be plotted against the peak ALT times the ULN, where the peak TBL and peak ALT may or may not happen on the same day of liver testing. The graph will be divided into 4 quadrants with a vertical line corresponding to 3x ULN for ALT and a horizontal line corresponding to 2x ULN for TBL. The upper right quadrant will be referred to as the potential Hy's Law quadrant, including potentially DILI cases.
- A similar graph will be plotted with respect to aspartate aminotransferase (AST).
- The individual patient profile of liver function tests (ALT, AST, alkaline phosphatase [ALP] and TBL) over time will be provided through a graph for all patients with peak value of ALT >3x ULN and peak value of TBL >2x ULN during the treatment period.
- Number (%) of patients will be provided for the following:
 - ALT or AST >3x ULN
 - ALT or AST >3x ULN and TBL >2x ULN
 - ALT or AST >3x ULN and TBL >2x ULN, and ALP < 2x ULN.

10. VITAL SIGNS AND PATIENT MEASUREMENTS

This section relates to Section 4.8.4 of version 1 of the SAP dated 08 July 2016.

Shift tables will present baseline value categories and post-baseline endpoint value categories as defined in [Table 3](#) of [Appendix A](#). The definitions for potentially clinically significant treatment-emergent values are defined in [Table 4](#) of [Appendix A](#).

Number (%) of patients with any post-baseline PCS vital sign values will be summarized by treatment group. A listing of patients who meet the threshold criteria will be provided.

11. 12-LEAD ELECTROCARDIOGRAMS (ECGS)

This section relates to Section 4.8.5 of version 1 of the SAP dated 08 July 2016.

A treatment-emergent PCS high value at any time will be defined as a change from a value less than or equal to the defined PCS value at baseline to a PCS high value at any post-baseline measurement. A treatment-emergent PCS low value at any time will be defined as a change from a value greater than or equal to the lower PCS value at baseline to a PCS low value at any post-baseline measurement. [Table 5](#) of [Appendix A](#) provides the PCS ECG values.

Number (%) of patients with post-baseline PCS ECG values will be presented by treatment group. A listing of subjects with potentially clinically significant changes in ECG values will be included.

Systolic Blood Pressure	≤90 mmHg	>90 mmHg to <160mmHg	≥160 mmHg
Diastolic Blood Pressure	≤50 mmHg	>50 mmHg to <100mmHg	≥100 mmHg
Pulse	≤50 beats/min	>50 beats/min to <90 beat/min	≥90 beats/min

Table 4: Potentially Clinically Significant Vital Signs Value Definitions

Vital Sign	PCS Low	PCS High
Systolic Blood Pressure	≤90 mmHg AND decrease of ≥20 mmHg; ≤90 mmHg; decrease of ≥20 mmHg	≥160 mmHg AND increase of ≥20 mmHg; ≥160 mmHg; increase of ≥20 mmHg
Diastolic Blood Pressure	≤50 mmHg AND decrease of >10 mmHg; ≤50 mmHg; decrease of >10 mmHg	≥100 mmHg AND increase of >10 mmHg; ≥100 mmHg; increase of >10 mmHg
Pulse	≤50 beats/min AND decrease of ≥15 beats/min; ≤50 beats/min; decrease of ≥15 beats/min	≥90 beats/min AND increase of ≥15 beats/min; ≥90 beats/min; increase of ≥15 beats/min

Table 5: Potentially Clinically Significant ECG Value Definitions

ECG Parameter	PCS Low	PCS High
PR Interval	<120 msec	>120 msec and increase >20 msec from baseline
QRS Interval	NA	>110 msec
QTc	NA	>500 msec

PRE-SPECIFIED LIST OF ADDITIONAL ANALYSES

REDUCE-IT STUDY

A Multi-Center, Prospective, Randomized, Double-Blind,
Placebo-Controlled, Parallel-Group Study to Evaluate the Effect of AMR101
on Cardiovascular Health and Mortality in Hypertriglyceridemic Patients
with Cardiovascular Disease or at High Risk for Cardiovascular Disease:
REDUCE-IT (Reduction of Cardiovascular Events with EPA – Intervention Trial)

Investigational Product: AMR101 (icosapent ethyl [ethyl-EPA])

Protocol Number: AMR-01-01-0019

Sponsor:

Amarin Pharma Inc.

[name]

[name]

[contact]

[contact]

Date: 15 August 2018

Version Number: Final 1.0

Confidentiality Statement

The information in this document is confidential and is not to be disclosed without the written consent of Amarin Pharma Inc., except to the extent that disclosure would be required by law and for the purpose of evaluating and/or conducting a clinical trial for Amarin Pharma Inc. You are allowed to disclose the contents of this document only to your Institutional Review Board or Independent Ethics Committee and study personnel directly involved with conducting this study. Persons to whom the information is disclosed must be informed that the information is confidential and proprietary to Amarin Pharma Inc. and that it may not be further disclosed to third parties.

SIGNATURE PAGE

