4.8.4 Vital Signs and Patient Measurements

Vital signs include systolic and diastolic blood pressures (mmHg), heart rate, respiration rate, and body temperature. Blood pressure should be measured for all patients at screening (Visit 1/ Visit 1.1), Randomization visit (Visit 2; Day 0) and all other follow-up visits including the last visit (end of the study. The end of the study will be at the time of the last patient's last visit of the follow-up period of the study).

Height is measured only at the screening visit (Visit 1). Vital signs (respiration, heart rate, temperature, systolic and diastolic blood pressure), height, and BMI by gender will be summarized descriptively at each scheduled visit. Mean and mean change from baseline values will be presented in a similar manner as for laboratory variables. Change from baseline will be calculated as post-baseline measurement minus baseline measurement. If either the baseline or post-baseline value is missing, the observation will not be included in the change from baseline summary. If there is more than one valid measurement for a selected visit after the baseline visit, the average of the values collected will be used.

All vital signs, height, and BMI, will be listed by patient, parameter, and time point.

4.8.5 12-Lead ECG

Twelve-lead ECG parameters including Heart Rate (bpm), PR Interval (msec), QRS Interval (msec), QT Interval (msec), and QTc Interval (msec) are measured, and Overall Interpretation and Silent MI (Yes/No) are summarized for all patients at Screening (Visit 1), Randomization visit (Visit 2; Day 0) and all other follow-up visits including the last visit of the study.

ECG parameters will be summarized using descriptive statistics. Mean and mean change from baseline values will be presented for every scheduled assessment. Change from baseline will be calculated as the post-baseline measurement minus the baseline measurement. If either the baseline or post-baseline value is missing, the observation will not be included in the change from baseline summary. In addition, counts and percentages for ECG overall interpretation (normal, abnormal, clinically significant and not clinically significant) and whether MI was present will be presented for each scheduled assessment.

ECG results will be listed by patient, parameter and time point.

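### SAP Addendum Table 5 uses 120 msec as both the low and the high PR cut, so under Section 11 a patient with baseline PR above 120 msec cannot be classed as treatment-emergent high

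*Combined protocol and SAP*

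**What the plan says.** Table 5 in Appendix A of the SAP Addendum gives the ECG thresholds. For PR interval, PCS low is below 120 msec and PCS high is ">120 msec and increase >20 msec from baseline". QRS (above 110 msec) and QTc (above 500 msec) have a high cut only.

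For a treatment-emergent PCS high value, Section 11 of the Addendum requires "a change from a value less than or equal to the defined PCS value at baseline to a PCS high value" on some later ECG. The mirror rule for low values requires a baseline "greater than or equal to the lower PCS value at baseline to a PCS low value at any post-baseline measurement".

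Section 11 then names two outputs. One is a count: "Number (%) of patients with post-baseline PCS ECG values will be presented by treatment group". The other is a listing of subjects with PCS changes in ECG values. Neither is restricted to treatment-emergent values.

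The laboratory rule in Section 9 of the Addendum is built differently. There the baseline has to be "less than or equal to the upper reference limit at baseline to a PCS high value at any post-baseline measurement", so the baseline condition uses the laboratory reference limit and not the PCS cut.

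Separately from Table 5, SAP Section 4.8.5 summarizes PR interval at each visit: "Mean and mean change from baseline values will be presented for every scheduled assessment". It also tabulates the overall ECG interpretation and lists ECG results by patient, parameter and time point.

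Table 1 of the same appendix sets the creatine kinase PCS-low limit at <30 U/L for women and <0.55 U/L for men.

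**The concern.** A PCS-high flag for PR should pick out patients whose PR interval has become long. A treatment-emergent version should pick out those who were not long at baseline and became so on study. With one number serving as both the low and the high limit, the PR scale has no range between the two flags. The treatment-emergent rule then asks for a baseline at or below what is also the low limit. It selects patients who leave the PCS-low range and passes over those who lengthen from any value above it.

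At stake is the meaning of one descriptive safety classification. PR is a planned ECG safety parameter, and the Addendum's reason for adding PCS flags is to identify individual outliers, which visit means do not do.

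**Working it through.** **Inputs.** PR PCS low: <120 msec. PR PCS high: post-baseline value >120 msec and a rise >20 msec (both Table 5). Treatment-emergent (TE) high: baseline at or below the defined PCS value, then a PCS high value (Section 11). The only number on the PR scale that can serve as the defined PCS value is 120. There is no stated figure to reproduce; this is a classification rule.

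**Rule in symbols.** Let b be the baseline and p a post-baseline value, in msec.

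- PCS high: p > 120 and p − b > 20.
- TE high: b ≤ 120, and PCS high.

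**Step 1: who can be TE high.** If b > 120 the first TE condition fails whatever p is. A baseline that is not PCS low has b ≥ 120. The two conditions b ≥ 120 and b ≤ 120 meet only at b = 120. Every other TE-high patient has b < 120 and so starts PCS low.

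| Baseline to post (msec) | Rise | Baseline PCS low? | PCS high? | TE high? |
|---|---|---|---|---|
| 180 to 260 | 80 | no | yes | no |
| 160 to 230 | 70 | no | yes | no |
| 121 to 230 | 109 | no | yes | no |
| 120 to 230 | 110 | no | yes | yes |
| 115 to 136 | 21 | yes | yes | yes |
| 110 to 131 | 21 | yes | yes | yes |
| 140 to 162 | 22 | no | yes | no |

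Enumerating whole-msec pairs with values up to 260 confirms this. For a baseline b from 121 to 239 there are 240 − b qualifying post values, and the sum of 1 to 119 is 7140. All 7140 pairs are PCS high and none is TE high. Adding b = 120 contributes 120 more pairs, all TE high. These are combinations of values, not patients.

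**Step 2: what the any-post-baseline count measures.** If b ≥ 100, then p − b > 20 gives p > b + 20 ≥ 120. The condition p > 120 is then automatically met, and PCS high becomes simply a rise above 20 msec. So 140 to 162 and 180 to 260 are counted alike. The 120 cut has an effect only when b < 100.

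**Step 3: comparison within the appendix.** Other parameters with numeric low and high limits keep them apart: potassium 3.0 and 5.5, sodium 130 and 150, platelets 100 and 500, systolic pressure 90 and 160, female hematocrit 37 and 42. Where a change-only criterion was wanted it was written as a separate item (Table 4, for example a systolic rise of ≥20 mmHg). QRS and QTc have no low cut, so the Section 11 rule works for them.

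**Step 4: effect of a distinct upper limit.** The documents give no upper limit for PR. As an assumption range only, take a high cut c of 180, 200, 210 or 220 msec and require b ≤ c, p > c and p − b > 20. In every case 160 to 230 becomes TE high and 110 to 131 does not. Of the 81 whole-msec baselines from 120 to 200, the number able to become TE high (post values up to 260) is 1 with the present cut, 61 with c = 180, and 81 with c = 200, 210 or 220.

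**Creatine kinase.** 30 / 0.55 is about 55, so the male low limit is about 55 times lower than the female one. In the other sex-specific low limits of Tables 1 and 2 the male value is equal or higher (female, male): creatinine 0.5, 0.65; uric acid 1.9, 2.5; red cells 3.5, 3.8; hemoglobin 10.0, 10.0; hematocrit 37, 42.

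**The case against.** The strongest objection concerns consequence. A reader might infer that the plan cannot detect PR prolongation. The documents do not support that. Section 11 defines treatment-emergent PCS values, but the outputs it names are the count with any post-baseline PCS value and a listing, and neither is limited to treatment-emergent values. A change from 180 to 260 msec is PCS high and enters the count. It also contributes to the mean changes in SAP Section 4.8.5 and appears in that section's listing. This part of the objection stands. What remains is that the count is non-specific (Step 2) and that any treatment-emergent split would be wrong.

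A reader might also infer a risk to the arrhythmia endpoint, whose definition includes high-level AV block. That does not follow. Those events are adjudicated by the Clinical Endpoint Committee (protocol Section 5.3, SAP Section 3.2.1) from clinical criteria, and do not depend on Table 5 flags.

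Third, the phrase for the defined PCS value might be read as the whole two-part PR criterion. No baseline can show a rise from itself, so on that reading 160 to 230 would be treatment-emergent. But a comparison of less than or equal to needs a number, so 120 is the more natural reading. That two readings give opposite classifications is itself a reason to clarify the text.

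Finally, two stronger statements are tempting and should be avoided. It is not strictly true that no patient outside the PCS-low range can qualify, because a baseline of exactly 120 msec can. Nor do the documents give a PR distribution, its ordinary variability or an upper normal limit, so no share of affected patients can be stated.

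**Conclusion.** The inconsistency is real and follows from the literal text. With 120 msec as both PR limits and the Section 11 baseline condition, no patient with a baseline above 120 msec can be classed as treatment-emergent PCS high. Apart from a baseline of exactly 120, only patients who start PCS low can be. The any-post-baseline count and the listing do capture prolongation, but from a baseline of 100 msec or more they cannot separate a prolonged PR from any other rise above 20 msec.

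The effect is confined to descriptive ECG safety flags. SAP Section 4.8 plans no formal treatment comparisons for safety data, and efficacy, alpha and sample size are untouched. The conclusion assumes that the defined PCS value for PR means 120 msec; it needs no outside PR limit. The correction is worth making but does not threaten the trial's conclusions.

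The male creatine kinase low limit is a separate, minor anomaly that appears to be on the wrong scale. Only the low flag is affected; the high bands, in multiples of the upper limit of normal, are intact.

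**What to change.** Before database lock and unblinding, reconcile Table 5 with Section 11 of the SAP Addendum:

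- Replace the PR PCS-high cut with an upper limit that the sponsor states and justifies, distinct from the 120 msec low limit. The documents supply none, so any figure, such as 200 msec, is an assumption until justified. Keep the rise above 20 msec.
- In Section 11, say that for PR the baseline condition for a treatment-emergent high value refers to that upper limit, so that the two-part criterion has one reading.
- State whether the ECG count is of all post-baseline PCS values, of treatment-emergent ones, or of both.
- Check the male creatine kinase PCS-low entry in Table 1 against its source and correct it if it is a transcription slip.

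The cost is two table cells and a sentence or two. PR values are already collected, so no new data or visits are needed.
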